Study protocol

**Sealed Therapeutic Shoe vs. Total Contact Cast as Treatment of Diabetic
Foot Ulcers: a Multicenter RCT**

Clinical Trial Registration Number: Unique Protocol ID: 18RS6667

Date: 9 September 2019

Background

Approximately 19-34 % of all people with diabetes will at some time in life develop a diabetic foot ulcer (DFU).¹ People with diabetes are especially prone to develop foot ulcers because of different diabetic complications, especially angiopathy and peripheral neuropathy.

The DFUs are often hard to heal and the treatment is long-lasting. The DFUs result in lower physical and mental quality of life and affects social relationships.² The treatment is also very costly,^{1,3} it has been estimated that 25-50 % of diabetic inpatient care is related to DFUs.⁴ Despite extensive treatment, all DFUs do not heal but some end in amputation. People with diabetes are at a 25-fold risk of amputation and every 20 second a person somewhere in the world has the foot amputated because of diabetes.⁵ 85 % of these amputations are preceded by a foot ulcer⁶ and many of these ulcers and amputation could have been prevented.⁷

Total contact cast (TCC) as gold standard treatment of DFUs

Plantar DFUs often are the result of a combination of foot deformities that increase plantar pressures when the person walks and that the person keeps walking despite high pressure and ulcers because he or she has lost sensation in the feet because of sensory neuropathy. Literature reviews and international guidelines^{8,9} recommend non-removable knee-high offloading devices, for example, a total contact cast (TCC) to treat plantar DFUs, as this offloads the ulcer from mechanical loading all day and night. Still, TCC is not accepted by all patients and is contraindicated in a number of cases because of negative side-effects. Most of these side-effects are the consequences of immobilizing the ankle joint, which impairs gait and results in lower ambulatory activity. For example, side-effects include reduction of joint flexibility, weight gain, muscle atrophy, sick leave from work and social isolation.¹⁰ In addition, a TCC can give secondary ulcers why weekly visits to the hospital is necessary to change casts. For these reasons, TCC is only used for a minority of the patients for whom it could be beneficial, despite being the gold standard treatment.¹¹

For working patients, casting often means sick leave from work, but casting can also be difficult for older patients with impairments of gait and balance. For patients where TCC is contraindicated or not tolerated, guidelines recommend removable offloading devices despite it is well known that these devices are not very effective.⁸ In practice, this means that many patients do not receive effective treatment. Another problem is that many patients get new foot ulcers after treatment with TCC,¹² in part because adherence to using therapeutic footwear after healing is lower than desirable.¹³

Sealed therapeutic shoe as alternative treatment

The investigators have developed a new treatment concept, sealed therapeutic shoe, which potentially can fill the need for effective ulcer treatment without limiting ambulatory activity with its associated negative consequences for physical, mental and social health, and to a lower cost, resulting in fewer obstacles for clinical use.

The concepts include therapeutic shoes with custom-made insoles, where the new part is how the insole is optimized to offload the ulcer from mechanical loading and that the shoe is "sealed" with a soft plastic strap and is used day and night, like a cast, and is only removed when changing the ulcer dressings. The ulcer is thereby offloaded but the person is free to ambulate and work as usual, and no cast changes are necessary. In addition to effective ulcer treatment and fewer side-effects the investigators hope that the positive experience of that high adherence to using therapeutic shoes results in healing will lead to higher adherence after healing, and thereby reduction of the risk of ulcer recurrences in the future.

The method to offload foot ulcers was first tested in a case-study, where it was found that the shoe and insole effectively offloaded the ulcer.¹⁴ After this the investigators evaluated the whole sealed shoe concept in a feasibility study on seven people with DFU. All ulcers healed and complications were few.¹⁷ The investigators are now going to evaluate the effects of sealed therapeutic shoes compared to gold standard treatment, that is, TCC.

Aims

The overarching aim is to evaluate whether sealed shoe can heal DFU at least as effectively as TCC, but with fewer adverse events during the treatment period, better long-term effects and to a lower cost.

Specific aims

Aim 1. To investigate whether a sealed shoe can heal DFUs at least as effectively as TCC.

Aim 2. To investigate whether there is a difference in adverse events during the treatment period with sealed shoe and TCC.

Aim 3. To investigate whether there is a difference in long-term effects (up to 12 months after end of treatment) with sealed shoe and TCC.

Aim 4. To investigate whether there is a difference in health economic outcomes between treatment with sealed shoe and TCC.

The null hypothesis is that a sealed therapeutic shoe does not heal DFUs as effectively as TCC, and that there are no differences between sealed shoe and TCC in adverse events, long-term effects and health economic outcomes.

Methods

The study is a non-inferiority multicenter randomized controlled trial (RCT).

Participants

Inclusion criteria: at least 18 years old, diagnosed diabetes mellitus (all types) and foot ulcer under metatarsal heads. A foot ulcer is here defined as "a break of the skin of the foot that includes minimally the epidermis and part of the dermis."¹⁵

Exclusion criteria: large ulcers (covering 3-5 metatarsal heads), toe pressure or TcPO₂ <30 mmHg, infection of IWGDF grade 3 (if uncontrolled or treatment has not been administered) or IWGDF grade 4, life expectancy <1 year, active Charcot foot, need of custom-made shoe,

and inability to read or write Swedish. In addition, people will be excluded where dementia, language- or other communication difficulties, active alcohol or substance abuse, or other factors increase the risk that adverse events will not be noted or reported, if the person does not have adequate social support.

The study is a randomized controlled non-inferiority trial where it will be investigated whether a new intervention (sealed shoe) is at least as effective as the established intervention (TCC).

Primary outcome is proportion of healed ulcers after 12 weeks of treatment. Based on the literature and our feasibility study the proportion of healed ulcers after 12 weeks treatment is estimated to 90% with sealed shoe or cast.^{16,17} If accepting $p=0.05$, a statistical power of 80% and a non-inferiority limit of 10%, 112 participants are needed. To compensate for attrition of participants, the aim is to recruit 150 participants. However, if it turns out that it is too difficult to recruit 150 participants, the recruitment of participant will end when the primary end point (healing at 12 weeks) has been observed for 56 participants per group, giving a total of 112 which fulfills the sample size calculation.

The participants will be randomized to treatment with sealed therapeutic shoe or TCC. The randomization will be stratified for ulcer size (smaller or bigger than 1 cm^2 , ulcer size calculated as longest diameter*longest perpendicular diameter) and study center, and use random permuted blocks of randomly varying size.

Recruitment of participants

People who fulfill the inclusion criteria and not the exclusion criteria will be given oral and written study information and asked about whether they are interested in participating in the study. Those who agree will sign an informed constant to participate.

Intervention group, sealed therapeutic shoe: A prosthetist/orthotist will try out new therapeutic shoes to the participants and make individual insoles after casts of the feet. There will a limited number of shoe types to choose between and the procedure and material for the insole production will be standardized. The ulcer will be offloaded by adjusting the insoles with the help of plantar pressure measurement using the F-scan system (Tekscan, Boston, MA, USA). The “seal” of the shoe consists of a soft plastic strip (Bracelok, DJO Nordic, Malmö) that have to be broken to remove the shoe.

[figure not shown]
Control group, TCC: The participants will be treated with TCC, applied in a standardized manner. Participants in this group will also receive shoes and insoles, according to the same protocol as above, before TCC treatment is initiated to be comparable to the other group in the long-term follow-up after healing, when both groups will use shoes and insoles to prevent reulceration.

Both groups will visit the cast technician 1-2 times/per week depending on the status of the ulcer. The cast technician will change dressings, note whether the seal has been broken (for the intervention group), change casts (for the control group), photograph and document ulcers and complications, and ask participants if they have experienced any issues with the treatment. After this, a new dressing is applied, and the shoe is sealed (intervention group) or

a new cast is applied (control group). Participants will use a cover on the shoe or cast while taking a shower, and for the intervention group a cover will also be used when sleeping. Both groups will receive written information about potential complications and contact information to the clinics.

Data collection

Participants in both groups will be assessed by a physiotherapist on five occasions (Figure 1): at base-line, four weeks into the treatment period, and then 1, 6 and 12 months after healing (when treatment is ended). For the 4 week into treatment and 1 month post-treatment assessments, a visit window of ± 1 week will be used. For the 6 and 12 months post-treatment assessments, a visit window of ± 1 month will be used. Standardized and validated instruments and assessment methods will be used for the data collection (Table 1).

Aim 1: Ulcer healing (primary end point)

Primary outcome measure is ulcer healing after 12 weeks of treatment, defined by the Food and Drug Administration (FDA) as full skin epithelization of the ulcer, confirmed by a second observation 14 days later.¹⁸ The cast technicians will assess ulcer healing in both the intervention group and control group. They will also photograph the ulcer and healed skin so a person blinded to group allocation can assess ulcer healing afterwards.

Aim 2: Adverse events during treatment (secondary end points)

Adverse events that are judged to be related to the offloading devices (shoe or TCC) will be classified as adverse device effects (ADE) and serious adverse device effects (SADE).³² ADE include, but are not limited to, skin abrasions, blisters, sleep disturbances, issues with gait and balance, etc. SADE include, but are not limited to, new foot ulcers that result in amputation (major amputation = above ankle, minor amputation = below ankle), sepsis, etc.

Adverse events that are not related to the offloading devices are classified as adverse events (AE) and serious adverse events (SAE).³² AE include, but are not limited to, skin abrasions, new foot ulcers on the contralateral foot and not related to the device, etc. SAE include, but are not limited to, death, amputation, onset of acute Charcot foot, sepsis, etc. (not related to the offloading device). However, in accordance with previous studies on this patient population, the investigators choose not to include all AE and SAE as the patient population suffers from multiple co-morbidities and therefore a high incidence of illness and hospital admissions unrelated to the DFU and offloading devices can be expected.³³ Therefore, all

ADE and SADE will be assessed, but only certain types of AE and SAE that are of particular interest, such as, amputation, death and onset of acute Charcot foot.

ADE, SADE, AE and SAE will be assessed with the aid of questionnaires, case report form (CRF), photographs of ulcer and skin, and patient files.

Aim 3: Long-term effects (secondary end points)

The secondary endpoints are time to healing and measures listed in Table 1. Each secondary endpoint is measured between one and five occasions during the study. For example, incidence of new foot ulcers, amputation, onset of acute Charcot-foot, death, adherence to using therapeutic shoes and locus of control will be assessed. Our hope is that the positive experience in the intervention group of that using therapeutic shoes can heal ulcers will result in a stronger internal locus of control and higher adherence to using therapeutic shoes after healing, so that fewer people will reulcerate or be affected by foot complications in the long term.

Data from patient files, questionnaires and the physiotherapists' assessments will be used for the analysis.

Aim 4: Health-economic outcomes (secondary end points)

The questionnaires RAND-36 and EQ-5D-5L will be used to assess general quality of life. Data from patient journals, Swedish Social Insurance Agency's system, and self-report questionnaires will be used to assess health care consumption and other costs.

Statistical analysis

See separate document for statistical analysis plan.

Research ethics

The participants will be informed about risks of the interventions in the written information that also will include contact information for the clinics. Risks will be minimized by excluding certain patient groups with heightened risks of side-effects not being noted or reported, and by a frequent follow-up during the intervention period. The study has been approved by the region ethics review board in Uppsala, Sweden (documents 2018/387 and 2019-03512).

Table 1. Overview of variables and assessment methods.

Variable	Assessment method	Assessment occasion					Specific aim
		Treatment period		Follow-up after treatment end			
		Base-line	4 weeks	1 month	6 months	12 months	
Ulcer healing	Clinical observation + blinded photo assessment	X	X	X			1
Skin complications	Clinical observation + blinded photo assessment	X	X	X			2
Glycemic control	Blood sample (HbA1c) ^a	X	X	X	X	X	2,3
BMI	Measurement of weight and height	X	X	X	X	X	2,3
Gait function	10 meter walk test ^{b 19}	X	X	X	X	X	2,3
Gait function	Timed up and go ^{b 20}	X	X	X	X	X	2,3
Balance	Berg balance scale ^{b 21}	X	X	X	X	X	2,3
Muscle atrophy	Calf circumference ^{a 22}	X	X	X	X	X	2,3
General quality of life	RAND-36 ^{c 23} , EQ-5D-5L ^{c 24}	X	X	X	X	X	2,3,4
Disease-specific quality of life	DFS-SF ^{c 25}	X	X	X	X	X	2
Physical activity	ActivPAL ^{d 26}	X	X	X	X	X	2,3
Physical activity	National Board of Health and Welfare's indicator questions ²⁷	X	X	X	X	X	2,3
Bone mass density	DXA ^e (heel bone)	X		X	X	X	2,3
Locus of control	Questions from MHLC-C ^{c 28}	X		X	X	X	2,3
Ankle range of motion	Goniometer ^{a 29}	X		X	X	X	2,3
Ankle strength	Dynamometer ^{a 30}	X		X	X	X	2,3
Adherence to therapeutic shoes	Questions from Q-TFA ^{c 31}	X		X	X	X	3
Treatment satisfaction	Visual analogue scale ^c		X	X			2
New ulcers, amputations, death, Charcot foot	Patient file and self-report ^c				X	X	3
Health care consumption	Patient administration systems and self-report ^c			X	X	X	4
Sick leave from work	Self-report, ^c Swedish Social Insurance Agency's system			X	X	X	4

^aStandardized method, ^bfunction test, ^cquestionnaire, ^dactivity monitor, ^eDual-energy X-ray absorptiometry

References

2. Vileikyte L. Psychosocial and behavioral aspects of diabetic foot lesions. *Curr Diab Rep* 2008;8(2):119-25.
4. Apelqvist J. Wound healing in diabetes. Outcome and costs. *Clin Podiatr Med Surg* 1998;15(1):21-39.
5. International Diabetes Federation, International Working Group on the Diabetic Foot. *Diabetes and foot care: time to act*. Brussels: International Diabetes Federation; 2005.

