2 STUDY METHODS

2.1 OVERALL DESIGN

The study is a randomized controlled trial with two parallel groups (intervention group using sealed shoe and control group using TCC) and an allocation ratio of 1:1.

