2.3 SAMPLE SIZE

The sample size calculation was performed using <http://powerandsamplesize.com/Calculators/Compare-2-Proportions/2-Sample-Non-Inferiority-or-Superiority>. Primary outcome is proportion of healed ulcers after 12 weeks of treatment. Based on the literature and our feasibility study the proportion of healed ulcers after 12 weeks treatment is estimated to 90% with sealed shoe or TCC.^{15, 16} If accepting $p=0.05$, a statistical power of 80% and a non-inferiority limit of 10%, 112 participants are

needed. To compensate for attrition of participants during the long-term follow up of secondary outcomes, the aim is to recruit 150 participants. The participants will be randomized to treatment with sealed therapeutic shoe or TCC. However, if it turns out that it is too difficult to recruit 150 participants, the recruitment of participant will end when the primary end point (healing at 12 weeks) has been observed for 56 participants per group, giving a total of 112 which fulfils the sample size calculation.

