3 STATISTICAL PRINCIPLES

3.1 CONFIDENCE INTERVALS AND P VALUES

In all analyses a 95% confidence level will be used as a cut off to declare statistical significance, and report both exact p-values and 95% CI. One-sided tests and CI will be used for the primary outcome and two-sided tests and CI the secondary outcomes. No adjustment for multiple comparisons will be used.

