6 STATISTICAL ANALYSES

6.1 ANALYSIS METHODS

6.1.1 ANALYSIS OF THE PRIMARY EFFICACY ENDPOINT(S)

Primary efficacy endpoint is ulcer healing at 12 weeks, defined as complete epithelialization which is maintained for a minimum of 14 days (as required by the FDA).³¹ Healing is thus a single endpoint assessed on a nominal scale.

Ulcer healing will be assessed by the cast technician at the local hospital who redress the DFU, approximately 1-2 times per week (depending on the status of the DFU) in both groups. The cast technician will also photograph the DFU so it can be assessed by another person, blinded to group allocation.

In the analysis of the primary endpoint, the ITT dataset (analyzed with and without adjustment for covariates) and the per protocol dataset (analyzed without adjustment for covariates only) will be used. For the non-adjusted analyses, crude risk ratio (RR) or OR will be calculated to assess the impact of offloading device type on ulcer healing. For the adjusted analysis, baseline variables (sex, age, education level, living conditions, diabetes type and duration, glycemic control, BMI, history of previous foot ulcers and amputations, foot deformities, index foot ulcer characteristics, number of active ulcers, use of tobacco, peripheral artery disease, and neuropathy, see point 5.1) will be included as candidates in a logistic multiple regression, using backward selection and a p-value of 0.10 as cut-off for removal.

Participants for whom the 12 week observation is missing will be categorized as “not healed”. The statistician conducting the analysis will be blinded to group allocation.

The proportion of healed ulcers in each study group will be calculated, and the results will be presented as RR or OR and corresponding 95% CI.

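### The protocol's 150 participants do not compensate for attrition in the primary analysis, because the SAP counts missing 12-week outcomes as failures

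*Protocol*

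**What the plan says.** The sample size text in the protocol (Participants) and in SAP 2.3 rests on one healing rate for both arms. The SAP puts it as "the proportion of healed ulcers after 12 weeks treatment is estimated to 90% with sealed shoe or TCC", and the protocol matches it. From that rate the protocol concludes: "If accepting $p=0.05$, a statistical power of 80% and a non-inferiority limit of 10%, 112 participants are needed". Both documents treat 112 as a total, 56 per group.

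They then give different reasons for the same recruitment target. The protocol says "To compensate for attrition of participants, the aim is to recruit 150 participants", with no qualification, directly after the primary-endpoint calculation. SAP 2.3 says "To compensate for attrition of participants during the long-term follow up of secondary outcomes, the aim is to recruit 150 participants".

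SAP 3.3 defines the ITT set as everyone randomized. SAP 6.1.1 sets the rule for absent data: "Participants for whom the 12 week observation is missing will be categorized as" not healed. Multiple imputation appears only as a sensitivity analysis (SAP 6.1.8 and 6.2). Neither sample size text mentions the not-healed rule or gives an expected 12-week missing rate.

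**The concern.** Adding recruits to cover attrition is normally sized on the idea that lost participants leave the analysis and the rest keep the design healing rate. Here they do not leave. They stay in the denominator as failures, which pulls the analysed rate below 90%. The variance of a proportion, p(1−p), rises quickly as p falls from 0.90: it is 0.090 at 0.90 and 0.154 at 0.81. With a fixed 10-point margin, power falls even if the two devices heal equally well.

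At stake is whether the power in the protocol and SAP describes the primary analysis that the SAP specifies. A funder or ethics board reading the protocol sentence would take 12-week losses to be covered. A reader of SAP 2.3 would take the extra participants to be meant for another purpose.

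**Working it through.** **Inputs.** Healing is 90% in each arm, the margin is 10 points, p=0.05 and power is 80% (protocol, Participants; SAP 2.3). The primary test is one-sided: "One-sided tests and CI will be used for the primary outcome and two-sided tests and CI the secondary outcomes" (SAP 3.1). SAP 2.1 gives "an allocation ratio of 1:1", so 112 is 56 per group and 150 is 75 per group. The ITT set is all randomized (SAP 3.3) and missing is not healed (SAP 6.1.1).

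**Assumptions not in the documents.** A share d has no 12-week observation, and d is equal in both arms. The 90% is the healing rate among those observed. There is no true difference between devices. The margin is applied to the difference in proportions, as in the sample size calculation. The range shown for d is 0 to 25%.

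**Reproducing the plan's figure.** With the usual normal approximation,

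n per group = 2p(1−p)(1.645+0.842)² / 0.10²

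At p = 0.90 this is 2 × 0.09 × 6.183 / 0.01 = 111.3, so 112 **per group**. The plan's number reproduces as a per-group figure and not as a total. That is a separate point, but it fixes the baseline used here.

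**Power under the missing-data rule.** The analysed rate is p = 0.90 × (1−d), with all n per group in the denominator, and

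power = Φ( 0.10 / √(2p(1−p)/n) − 1.645 )

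For example, at n = 75 and d = 10%, p = 0.81 and p(1−p) = 0.1539. The standard error is √(2 × 0.1539/75) = 0.0641, and power is Φ(1.561 − 1.645) = 47%.

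| Missing at 12 weeks | Analysed rate | 56 per group | 75 per group | 112 per group |
|---|---|---|---|---|
| 0% | 90.0% | 55% | 65% | 80% |
| 5% | 85.5% | 44% | 54% | 68% |
| 10% | 81.0% | 38% | 47% | 60% |
| 25% | 67.5% | 30% | 37% | 48% |

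**Does the usual inflation restore power?** Dividing 112 per group by (1−d) gives 118, 125 and 150 per group at 5, 10 and 25% missing. Power at those sizes, under missing = not healed, is 70%, 64% and 58%. Holding 80% would take 154 per group at 5% and 191 at 10% (the same n formula at p = 0.855 and 0.81).

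**When do the extra recruits offset the rule?** Compare 75 per group under the rule with 56 per group and nothing missing (55%). Power is equal when p(1−p)/75 = 0.09/56, so p(1−p) = 0.1205 and p = 0.8598. Then d = 1 − 0.8598/0.90, or about 4.5%.

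**Unequal loss.** At 75 per group with 5% missing on the shoe and 10% on the cast, the analysed rates are 85.5% and 81.0%. The standard error is √((0.1240+0.1539)/75) = 0.0609, and power is Φ((0.10+0.045)/0.0609 − 1.645) = 77%. With the losses reversed it is Φ((0.10−0.045)/0.0609 − 1.645) = 23%.

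**The case against.** Several stronger conclusions are tempting, and the documents do not support them.

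- *Extra recruits cannot restore power.* They always help under equal loss: at 10% missing, 75 per group gives 47% against 38% at 56. A large enough trial reaches 80%. What fails is inflation by 1/(1−d), which is too small for this rule.
- *Any loss makes non-inferiority harder to show.* That needs roughly equal loss. The protocol's Background says the cast is not accepted by all patients, so heavier loss on the cast is plausible, and the rule would then favour the shoe.
- *The plan expects to lose 38 of 150, or 25.3%, by 12 weeks.* That is only the subtraction 150 − 112. SAP 2.3 ties the margin to long-term follow-up. Ulcers are to be seen one to two times a week, so low 12-week missingness is quite possible.
- *There is no allowance at all for 12-week losses.* All 150 would enter the ITT analysis whatever reason is given for recruiting them, and the fallback rule counts participants whose endpoint has been observed, 56 per group.
- *The rule takes power down from 80%.* For the plan as written, power is 55% at 56 per group and 65% at 75, before any data are missing. The larger shortfall comes from reading a per-group number as a total.

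A further objection stands in part. If the 90% in the cited sources already counts dropouts as failures, multiplying by the share observed counts them twice. The documents do not say which it is. The plan adds attrition on top of 112 and, in the fallback, counts observed endpoints, which points to a rate among those observed, but this remains an assumption.

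**Conclusion.** The protocol's statement that 150 participants compensate for attrition does not hold for the ITT analysis in SAP 6.1.1, and it conflicts with the purpose that SAP 2.3 gives for the same number. At the planned 75 per group, power falls from 65% with complete data to 54%, 47% and 37% at 5, 10 and 25% missing. The added participants make up for the rule, measured against 55% at 56 per group, only below about 4.5% missing. The problem is independent of the per-group error: at 112 per group, power goes from 80% to 68%, 60% and 48%.

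These figures rest on equal loss in both arms, on 90% being the rate among those observed, and on an assumed range of missing rates. If 12-week follow-up is nearly complete the effect is small. If loss differs between arms it can go either way. It is secondary to the error over 112, but should be corrected along with it.

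**What to change.** In the protocol's sample size paragraph and in SAP 2.3, restate the power of the primary ITT analysis at the group sizes that will actually be used. Give it for 0, 5, 10 and 25% missing under missing = not healed. State that loss is taken as equal in both arms and that 90% is taken as the rate among those observed. A line showing unequal loss would tell readers that the rule is not always conservative.

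Remove the protocol's claim that 150 compensates for attrition in the primary analysis, and give the 150 one purpose in both documents.

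The cost is wording and a less favourable stated power. No extra patients are needed for this change. It makes the plan's power statement accurate but does not raise the power.
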